9.5.2 Safety analyses

Safety analyses will be performed using the safety analysis set.

AEs will be coded using the most recent version of the Medical Dictionary for Regulatory Activities that will have been released for use by AstraZeneca/designee.

Safety data will be presented by using descriptive statistics and by cohort unless otherwise specified.

AEs will be presented for each cohort by System Organ Class and/or Preferred Term covering the number and percentage of subjects reporting at least 1 event and the number of events where appropriate.

AEs occurring prior to the start of IP and treatment-emergent AEs will be presented separately.

An overview of AEs will be presented for each cohort. The number and percentage of subjects with any AE, AEs with outcome of death, SAEs, AEs leading to discontinuation of IP, AEs leading to IP dose interruptions, AEs leading to IP dose reduction and AEs leading to

withdrawal from study, as well as the number of individual occurrences in those categories, will be presented.

Separate AE tables will be provided taking into consideration causal relationship as assessed by the investigator, CTCAE grading, seriousness, death and events leading to discontinuation of IP as well as other actions taken related to IP, AEs of special interest, and other significant AEs.

An additional table will present the number and percentage of subjects with the most common AEs (frequency of >10%).

Key subject information will be presented for subjects with AEs with an outcome of death, SAEs, and AEs leading to discontinuation of IP.

An AE listing for the safety analysis set will cover details for each individual AE.

Full details of AE analyses will be provided in the SAP.

The following events are considered to be treatment-emergent:

- AEs with an onset date on or after the first dose of IP and within 30 days after the last dose of IP.
- Worsening of pre-existing events on or after the first dose of IP and within 30 days after last dose of IP.

Laboratory data (haematology, clinical chemistry and quantitative urinalysis) will be summarised using descriptive statistics over time in terms of absolute values and changes from baseline. Shift tables showing CTCAE grade changes from baseline on treatment will be produced by laboratory parameter for haematology and clinical chemistry.

All vital signs and height, weight and BSA will be summarised using descriptive statistics over time in terms of absolute values and change from baseline.

Other safety assessments (pregnancy test, physical examination, ECG, echocardiogram, ophthalmologic examination, performance status, bone growth monitoring and Tanner staging) will be listed and summarised where appropriate. Box plots of laboratory and vital signs data may be provided if needed.

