3. OBJECTIVES AND ENDPOINTS

Table 2Study objectives

Primary objectives:	Endpoints:	
To assess the safety and tolerability of selumetinib in Chinese paediatric and adult subjects with NF1 and inoperable PN	 Paediatric and adult cohorts: Safety and tolerability will be evaluated in terms of AEs, clinical safety laboratory assessments, physical examination, vital signs, height/weight, ECG, echocardiogram, ophthalmologic assessment and performance status. Paediatric only: Safety and tolerability will also be evaluated in terms of bone growth and Tanner stages. 	
	Assessments related to AEs will include:	
	Occurrence/frequency.	
	• Relationship to IP as assessed by investigator.	
	CTCAE grade.	
	• Seriousness.	
	• Death.	
	• AEs leading to discontinuation of IP.	
	• AEs of special interest.	
To characterise the PK of selumetinib and its metabolite (N-desmethyl selumetinib) in Chinese paediatric and adult subjects with	PK parameters for selumetinib and N-desmethyl selumetinib will be derived following single dose and multiple doses. These may include, but are not limited to:	
NF1 and inoperable PN	After a single dose:	
	• AUC.	
	• AUC ₀₋₁₂ .	
	• AUC _{0-t} .	
	• C _{max} .	
	• t _{max} .	
	• t _{1/2} .	
	After multiple doses:	
	• AUC _{0-12,ss} .	
	• C _{max,ss} .	
	• Rac.	

Secondary objectives:	Endpoints:	
To evaluate the clinical efficacy of selumetinib in Chinese paediatric and adult subjects with NF1 and inoperable PN on ORR, DoR, PFS, TTP, and TTR	ORR is defined as the proportion of subjects who have a complete response or confirmed partial response (defined as a target PN volume decrease ≥20% compared to baseline, confirmed by a consecutive scan within 3 to 6 months after first response, as determined by the investigator and independent central review per Response Evaluation in Neurofibromatosis and Schwannomatosis (REiNS) criteria.	
	DoR is defined as the time from the date of first documented response (which is subsequently confirmed) until the date of documented progression or death in the absence of disease progression, as determined by the investigator and independent central review per REiNS criteria.	

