5.1 Inclusion criteria

Subjects are eligible to be included in the study only if all of the following inclusion criteria apply:

Informed consent

1 Capable of giving signed informed consent which includes compliance with the requirements and restrictions listed in the ICF and in this CSP.

Paediatric cohort: parent/legal guardian consent is required, where possible involving the paediatric subject in the assent process with appropriate documentation.

2 Provision of signed and dated written ICF prior to any mandatory study-specific procedures, sampling, and analyses.

Paediatric cohort: mandatory provision of signed and dated parent/legal guardian consent for the study along with the paediatric assent form, when applicable. For subjects who reach the age of legal consent during the clinical study, notification may be required and a new consent form may need to be signed by the subject.

The ICF process is described in Appendix A 3.

Age

3 Paediatric cohort: Chinese subjects ≥3 years and <18 years of age with a BSA ≥0.55 m² at the time of study enrolment who are able to swallow whole capsules. There must be a

CONFIDENTIAL AND PROPRIETARY 42 of 183

minimum of 6 subjects each in the 3 to 11 and 12 to 17 year age groups at the time of enrolment.

Adult cohort: Chinese subjects ≥ 18 years of age at the time of study enrolment who are able to swallow whole capsules.

Disease diagnosis

- 4 All study subjects must be diagnosed with (i) NF1 per NIH Consensus Development Conference Statement 1988 and (ii) inoperable PN. In addition to PN, subjects must have at least 1 other diagnostic criterion for NF1 (NIH Consensus Development Conference Statement 1988):
- Six or more café-au-lait macules >5 mm in greatest diameter in pre-pubertal individuals and >15 mm in greatest diameter in post-pubertal individuals.
- Freckling in the axillary or inguinal regions.
- Optic glioma.
- Two or more Lisch nodules (iris hamartomas).
- A distinctive osseous lesion such as sphenoid dysplasia or tibial pseudarthrosis.
- A first-degree relative with NF1.

A PN is defined as a neurofibroma that has grown along the length of a nerve and may involve multiple fascicles and branches. A histologic confirmation of the tumour is not necessary in the presence of consistent clinical and radiographic findings, but should be considered if malignant degeneration of a PN is clinically suspected.

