8.2.4 Height and weight

Height and weight will be measured at the times outlined in Table 1. The subject's height will be recorded in centimetres (cm) and weight will be recorded in kilograms (kg). Height and weight measurements will be performed in light clothing and with shoes off. CONFIDENTIAL AND PROPRIETARY 72 of 183
For paediatric subjects:

Collect all available documented previous height and weight measurements and growth curves if available at screening.

Height: The subjects should take off shoes and socks, and heels should be placed against a wall with ankles together. Height should be measured in a standing position with a stadiometer. Height measurements should be taken at approximately the same time of day for each visit, when possible. The height should be plotted on a standardised growth chart. In subjects with known leg length discrepancy due to limb hypertrophy, height should be measured with the subject bearing weight on the limb without hypertrophy.

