8.2.9 X-ray in paediatric subjects

Yearly growth assessments require integration of information including height measurements, puberty staging (Tanner staging), and bone age if clinically indicated, which should be plotted onto growth charts. Children with impaired growth velocity should be referred to a paediatric endocrinologist as clinically indicated for evaluation, and should be followed until they reach final adult height.

An X-ray of the hand and wrist will be performed at screening and at other visits/cycles if clinically indicated, as specified in Table 1, to monitor growth plates and the potential risk of physeal dysplasia.

The investigator should regularly look for signs of physeal dysplasia (e.g. joint pain and fatigue after exercising, abnormal gait, and spine irregularities) in the paediatric population. Children who show signs of physeal dysplasia at the time of selumetinib discontinuation should have a follow-up assessment after 30 days to evaluate the potential for reversibility.

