9.2 Sample size determination

The primary objectives are to evaluate the safety, tolerability and PK of selumetinib. Approximately 16 paediatric and 16 adult subjects with NF1 and inoperable PN will be enrolled in the study to obtain adequate PK and safety data. Per the Chinese Phase 1 PK guideline, at least 8 to 12 subjects per cohort are required. To allow for dropouts and nonevaluable cases, 16 subjects in each cohort will be enrolled. There must be a minimum of 6 subjects each in the 3 to 11 and 12 to 17 year age groups at the time of enrolment.

9.3 **Populations for analyses**

Population	Description
Safety analysis set	The safety analysis set consists of all subjects who receive at least 1 dose of selumetinib.
Pharmacokinetic analysis set	All subjects who receive at least 1 dose of selumetinib and have at least 1 post-dose evaluable concentration-time data point.

For purposes of analysis, the following populations are defined:

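### Height and weight are summarised only as raw values and raw change, which cannot reliably show moderate growth impairment in an uncontrolled cohort aged 3 to under 18

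*Protocol*

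**What the plan says.** Section 9.5.2 sets the scale in one sentence for both cohorts: "All vital signs and height, weight and BSA will be summarised using descriptive statistics over time in terms of absolute values and change from baseline". The synopsis repeats it. The next sentence in 9.5.2 deals separately with other assessments, including "performance status, bone growth monitoring and Tanner staging) will be listed and summarised where appropriate".

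Table 2 in Section 3 makes these primary safety measures. For both cohorts it lists "physical examination, vital signs, height/weight, ECG, echocardiogram, ophthalmologic assessment and performance status", and for children it adds: "Paediatric only: Safety and tolerability will also be evaluated in terms of bone growth and Tanner stages".

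The paediatric cohort is "Chinese subjects ≥3 years and <18 years of age" (Section 5.1), about 16 children, and Section 9.2 requires that "There must be a minimum of 6 subjects each in the 3 to 11 and 12 to 17 year age groups". The study is open label and not randomised (Section 6.3.1), and the two cohorts are analysed separately (Section 9.5).

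Growth is followed child by child. Section 8.2.4 says "The height should be plotted on a standardised growth chart", and Section 8.2.9 says "Children with impaired growth velocity should be referred to a paediatric endocrinologist as clinically indicated for evaluation". No standardised score, percentile or growth velocity is named as an analysis variable anywhere in Section 9.

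**The concern.** A change from baseline is informative when the expected change is known. For adult height it is about zero. For a child it may be almost nothing or many centimetres, according to age, sex and pubertal stage. With no control arm, nothing in the planned table shows what the children should have gained.

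The cohort mean therefore depends mainly on normal growth and on how many younger children happened to enrol. A child who grows at half the expected rate still contributes a positive change. The protocol itself treats growth as a concern: physeal dysplasia is a paediatric adverse event of special interest, and height and weight continue to be measured in the one-year paediatric follow-up. The stated group summary of a primary endpoint should be able to address that concern.

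**Working it through.** The protocol gives no growth figure to reproduce. The check is an illustration, and its velocities and SDs are assumptions.

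**Inputs from the protocol.** 16 children, at least 6 in each age band, so 6 to 10 are aged 3–11. Cycles last 28 days. The primary data cut-off is at the end of Cycle 10 and the final one at the end of Cycle 24 for the last subject dosed.

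- Cycle 10: 10 × 28 = 280 days; 280/365.25 = 0.77 years.
- Cycle 24: 24 × 28 = 672 days; 672/365.25 = 1.84 years. Adding the 2 days of Cycle 0 gives study day 674, as in Table 1.

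**Assumed inputs.** Normal velocity 5–7 cm/year at ages 3–11 and 1–6 cm/year at ages 12–17. Reference SD of height for age 4.5–7 cm. SD of change in SDS 0.3–0.5.

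**Mean raw height gain** = [n × v(young) + (16 − n) × v(old)]/16 × years × (1 − reduction).

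- Lowest normal value at Cycle 24: (6 × 5 + 10 × 1)/16 × 1.84 = 4.6 cm.
- Highest: (10 × 7 + 6 × 6)/16 × 1.84 = 12.2 cm.

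| Growth | Cycle 10 | Cycle 24 |
|---|---|---|
| Normal | 1.9–5.1 cm | 4.6–12.2 cm |
| Slowed by 25% | 1.4–3.8 cm | 3.5–9.1 cm |
| Slowed by 50% | 1.0–2.5 cm | 2.3–6.1 cm |

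Every value is positive and the ranges overlap.

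**Age mix alone.** Take normal growth at 6 cm/year (younger) and 1 cm/year (older). With 6 younger children the Cycle 24 mean is (36 + 10)/16 × 1.84 = 5.3 cm. With 10 it is (60 + 6)/16 × 1.84 = 7.6 cm. The 2.3 cm difference has nothing to do with treatment.

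**Two cohorts with the same mean.** Take 8 younger and 8 older children, the younger normally growing 6 cm/year. If the older normally grow 3 cm/year and all growth is normal, the mean is 4.5 × 1.84 = 8.3 cm. If the older normally grow 6 cm/year and all growth is slowed by 25%, the mean is 6 × 0.75 × 1.84 = 8.3 cm.

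**The standardised scale.** A child expected to grow 6 cm/year who grows at half that rate gains 3 × 1.84 = 5.5 cm by Cycle 24 and is 5.5 cm short. On the raw scale this is a gain. On the SDS scale it is a fall of 5.5/7 to 5.5/4.5, or 0.8 to 1.2. By Cycle 10 the shortfall is 3 × 0.77 = 2.3 cm, a fall of 0.3 to 0.5.

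For the cohort, a 25% slowing loses 0.25 × 4.6 to 0.25 × 12.2, or 1.2 to 3.0 cm, by Cycle 24. That is very roughly 0.2 to 0.7 SDS. The 95% CI half-width with 16 children is 2.13 × 0.3/4 = 0.16 to 2.13 × 0.5/4 = 0.27 SDS. Standardising supplies the missing expected value, about zero. It does not guarantee detection at the low end of the range.

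**The case against.** The strongest reply is that this is SAP detail. Section 9.5 calls itself a summary, a full SAP is to follow, and nothing in 9.5.2 rules out standardised scores. The SAP may indeed add them. But the protocol does not leave the scale open: it states one, and that scale suits adults better than children.

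A reader might infer that growth harm would go unseen. The documents do not support that. Height is plotted on growth charts, impaired velocity prompts referral, and Section 8.2.9 asks investigators to look regularly for signs of physeal dysplasia. Short stature is a defining term for that event of special interest, and separate tables of such events are planned. These are real safeguards for the individual child. They depend on recognition and reporting at the site, however, and do not give a group estimate of growth.

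A reader might also infer that raw height is the only planned analysis of bone growth. It is not: bone growth and Tanner stage have their own summary line, though it names no metric. The firmer ground is that height/weight is itself a primary safety endpoint.

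Two further objections stand. The sizes rest on assumed velocities and SDs. Raw summaries also remain useful, since BSA determines dose and is calculated from weight in children.

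**Conclusion.** The point holds in a limited form. For children, Section 9.5.2 names a scale on which mean change mostly reflects normal growth and age mix. With no control arm it cannot reliably show moderate growth impairment. It would be too strong to say that it can show none: near-arrest of growth would be visible.

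Under the assumed velocities, the Cycle 24 ranges for normal growth and for a 25% slowing share the interval from 4.6 to 9.1 cm. Other velocities would move these limits. The main conclusion needs only that normal growth differs widely between ages 3 and 17 and that the study has no comparator. The primary safety summary should be improved, but the design and data collection are not at fault.

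**What to change.** In Section 9.5.2 and the matching synopsis text, add for the paediatric cohort:

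- change from baseline by visit in age- and sex-specific SDS for height and for weight;
- annualised height velocity, with the interval stated, because over short intervals measurement error dominates (a 1 cm error becomes 1/0.31 = 3.3 cm/year at Cycle 4, where 4 × 28/365.25 = 0.31 years, but 1/1.84 = 0.5 cm/year at Cycle 24);
- both shown for the 3–11 and 12–17 year groups as well as overall.

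Name one growth reference. Section 8.2.4 asks for a standardised chart but does not say which. Keep the raw summaries of height, weight and BSA alongside. The earlier heights and growth curves that Section 8.2.4 collects where available could support a comparison of each child's velocity before and during treatment.

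The cost is choosing the reference and programming the lookup. Age, sex, height and weight are already collected, so no visit or procedure is added. A population reference is not a concurrent control, and each age group will have only 6 to 10 children, so the results remain descriptive.

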9.5.3 Efficacy analyses

Efficacy analyses will be performed using the safety analysis set.

CONFIDENTIAL AND PROPRIETARY 92 of 183

Efficacy endpoints (ORR, DoR, PFS, TTR and TTP) based on independent central review and investigator assessments will be analysed separately. The discordance between the independent central review and the investigator will be provided.

ORR will be presented with corresponding 2-sided exact 95% CI based on the Clopper-Pearson method (Clopper and Pearson 1934). Descriptive statistics will be provided for BOR. Change in PN growth will be evaluated descriptively by summaries of percentage and absolute change in PN volume from baseline. The best percentage change from baseline will be summarised descriptively and presented graphically using waterfall plots. Spaghetti plots showing individual subject tumour volume and percentage change in tumour volume will also be produced.

Kaplan-Meier plots of DoR, PFS, TTR and TTP will be presented. The median DoR, PFS, TTR, TTP and 95% CI will be calculated using the Kaplan-Meier method.

For analysis of disfigurement, anonymised photographs of PN-related morbidity will be provided in the individual subject reviews, where appropriate.

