PNs in NF1 patients are histologically benign Schwann-cell tumours (Wu et al 2005; Rutkowski et al 2000) that, depending on the location and the growth rate, bear all the characteristics typical of cancers. There is a high unmet medical need for patients with NF1 and inoperable PN as there are no approved medical treatments to cure, prevent or reverse the disease. A number of medical treatments have undergone evaluation in early clinical studies for subjects with NF1-related PNs, but these studies have reported only moderate to no clinical activity, and no systemic therapy has been shown to induce consistent and durable tumour shrinkage. Since these relentlessly growing tumours induce co-morbidities that impact children from early childhood through adolescence and their entire lifespan, patients with inoperable and progressive PNs suffer from a significant unmet medical need. There are no epidemiological data to estimate the actual incidence or prevalence of NF1 in China. It is believed that the clinical picture of NF1, including NF1 and inoperable PN, in China is in line with that observed globally. Debulking surgery, which is complex and difficult, is the only available treatment for suitable patients with PN, who are always in a distressing condition both physically and mentally. Only a few patients may eventually receive surgery. There is therefore a significant unmet medical need for patients with NF1 and inoperable PN in China.

In the clinical setting, treatment with selumetinib in the Phase 1 SPRINT study resulted in confirmed partial responses (PRs; tumour volume decreases from baseline of \geq 20%) in 16/24 (66.7%) children. The response rate was confirmed in SPRINT Phase II Stratum 1. The overall response rate by NCI POB central analysis was 66% (95% CI: 51.2, 78.8; 33/50 patients). Median time to response is 8 cycles. For responders, 42.4% (14/33 patients) achieved response at cycle 5, 72.7% (24/33 patients) achieved response at cycle 9, 97% (32/33 patients) achieved response at cycle 13. Importantly, improvements in PN-related pain and motor impairment demonstrated that selumetinib provided clinical benefit. Selumetinib, therefore, has promising clinical activity for the treatment of NF1 and inoperable PN, as well as a favourable safety profile.

A detailed description of the chemistry, pharmacology, efficacy, and safety of selumetinib is provided in the Investigator's Brochure.

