9.4.3.1.5 Time to response

Time to response (TTR) is defined as the time from the date of first dose until the date of the first documented response (which should be subsequently confirmed if it's a partial response), as determined by independent central review and investigator per REiNS criteria.

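### A Kaplan-Meier median for time to response on all treated subjects mixes response rate with speed of response; summarise TTR in confirmed responders instead (minor)

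*Protocol*

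**What the plan says.** Section 9.4.3.1.5 gives the endpoint: "Time to response (TTR) is defined as the time from the date of first dose until the date of the first documented response", with confirmation required for a partial response. It gives no end date for a subject who never responds.

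Section 9.5.3 sets the population, "Efficacy analyses will be performed using the safety analysis set", and names TTR among the efficacy endpoints. The populations table in Section 9.3 defines that set: "The safety analysis set consists of all subjects who receive at least 1 dose of selumetinib". Section 9.5.3 then plans Kaplan-Meier plots for TTR and adds "The median DoR, PFS, TTR, TTP and 95% CI will be calculated using the Kaplan-Meier method".

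Section 2.2 (Background) reports SPRINT Phase II Stratum 1: 33 of 50 patients responded, and "Median time to response is 8 cycles. For responders, 42.4% (14/33 patients) achieved response at cycle 5". It goes on to 24/33 by cycle 9 and 32/33 by cycle 13.

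**The concern.** A Kaplan-Meier estimate needs a risk set and a rule for subjects without the event. If the risk set is all dosed subjects, never-responders are censored, and two things follow.

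- The median is the time at which half of everyone treated has responded. A cohort that responds just as fast but less often shows a later median, or none.
- Kaplan-Meier treats a censored subject as having the same later chance of responding as those still at risk. That is reasonable for a subject still under follow-up at the data cut-off. It is not reasonable after progression, and it is impossible after death. Censoring there pushes the estimated cumulative response above the proportion who actually respond.

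At stake is how a named secondary endpoint reads. A later or inestimable median could be taken for slow response when it reflects the response rate or the times at which non-responders left.

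**Working it through.** **Inputs.** From Section 2.2: 33/50 responders, with 14, 24 and 32 of the 33 by cycles 5, 9 and 13. From Section 9.2: 16 subjects per cohort. From Section 9.5: the primary data cut-off gives every subject the chance of at least 10 cycles.

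**Assumptions.** Cycles 5, 9 and 13 are read as the scans after 4, 8 and 12 completed cycles. The one remaining responder is placed at 16 cycles, which affects no median below. The median is the first time at which S(t) ≤ 0.5.

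**Formula.** S(t) = product over scan times of (1 − responses / number at risk). Responses are 14, 10, 8 and 1 at 4, 8, 12 and 16 cycles.

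**Step 1. Reproduce the protocol's figure (33 responders only).**
- S(4) = 19/33 = 0.576
- S(8) = 9/33 = 0.273
- Median 8 cycles, as Section 2.2 states.

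**Step 2. All 50, with the 17 non-responders censored after the last response.**
- S(4) = 36/50 = 0.72
- S(8) = 0.72 × 26/36 = 0.52
- S(12) = 0.52 × 18/26 = 0.36
- S(16) = 0.36 × 17/18 = 0.34
- Cumulative response is 28%, 48%, 64% and 66%, so the median is 12 cycles.

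**Step 3. Change only the censoring times.**

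| Non-responders censored between the Cycle 4 and Cycle 8 scans | At risk at Cycle 8 | S(8) | Median |
|---|---|---|---|
| 0 | 36 | 0.520 | 12 |
| 3 | 33 | 0.72 × 23/33 = 0.502 | 12 |
| 4 | 32 | 0.72 × 22/32 = 0.495 | 8 |
| 5 | 31 | 0.72 × 21/31 = 0.488 | 8 |

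If everyone is cut at 10 cycles, S stays at 0.52 and the median is not reached.

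**Step 4. Dependence on the response rate.** Hold the responders' timing fixed and allow no early censoring. The full-set median is 8 cycles only if ORR × 24/33 ≥ 0.5, that is ORR ≥ 68.75%. It is 12 cycles or less only if ORR × 32/33 ≥ 0.5, that is ORR ≥ 51.6%.

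**Step 5. One cohort of 16, complete follow-up.** The median is reached once 8 subjects have responded, so P(not reached) = P(fewer than 8 of 16).
- ORR 66% (SPRINT): 0.056
- ORR 50% (assumed): 0.402

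At SPRINT rates the median is 8 cycles or less with probability 0.53 and 12 cycles with probability 0.39. If all 16 were cut at exactly 10 cycles, P(fewer than 8 of 16 at 48%) = 0.47. That is a limiting case, because subjects enrolled earlier will have longer follow-up.

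**The case against.** The strongest reply is that the premise is inferred. No sentence says non-responders are censored. The Kaplan-Meier sentence also covers DoR, which exists only in responders, so the safety set cannot be the literal risk set for every endpoint listed. Section 9.5 calls itself a summary and leaves analysis populations to the SAP, which is not shown here. If TTR is restricted to responders there, Kaplan-Meier returns the 8 cycles of Step 1. This lowers the weight of the point but does not remove it. DoR starts at response and so restricts itself. TTR starts at first dose and does not, and Section 9.5.3 fixes both the set and the method.

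A second reply is that time to response in all treated subjects is a legitimate descriptive quantity, and that ORR, best overall response and waterfall plots are reported alongside. That stands, provided the quantity is estimated with progression and death handled as competing events and is labelled for what it is.

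Third, early informative censoring may be limited. Section 4.3 reports no SPRINT patient with progression as best response, and scans continue for about a year after stopping for other reasons, if clinically applicable. This bears on the size of the overstatement, not on the mixing of rate and speed.

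A reader might also infer that the trial's TTR will be set against SPRINT's and will look falsely slow. The documents do not support that. The SPRINT figure is background, no TTR comparison is planned, and Section 9.1 says no formal hypotheses are tested. Nor does Section 2.2 label the 8-cycle median as responder-only: "Median time to response is 8 cycles" stands alone, and only the next sentence speaks of responders. A responder median fits the counts, but so does a full-set estimate with four early censorings.

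**Conclusion.** The point holds as a minor one. As written, Section 9.5.3 yields a TTR median that depends on response rate, response speed and the censoring times of non-responders together. On one set of SPRINT counts it can be 12 cycles, 8 cycles or not reached, while responders' median stays at 8. In a cohort of 16 with complete follow-up, the chance of no median is about 6% at an ORR of 66%. The 40% figure requires an assumed ORR of 50%.

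This rests on the literal reading of the safety set, on the scan-time reading of cycles 5, 9 and 13, and on the stated median convention. A reader might go further and say that the curve would climb to 100% response. That happens only if all 17 non-responders are censored before the last responder, who is then alone at risk at an assumed Cycle 16. It should not be used as a measure of the problem. No primary objective or formal test is affected.

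**What to change.** In Section 9.5.3, remove TTR from the two Kaplan-Meier sentences (plot and median). State instead that TTR is summarised in confirmed responders: number, median, range, and number first responding by each scheduled scan, presented next to ORR. If an all-subject curve is wanted, show the cumulative incidence of confirmed response in the safety analysis set, with progression and death as competing events and subjects still under follow-up censored at the data cut-off. Carry the same wording into the SAP.

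The cost is a sentence or two and one table, with no new data. The downside is that a responder summary is conditional on response and says nothing about how many respond, so it must be read with ORR.
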